5.4 Interim contacts and unscheduled visits

The participant or the investigator may request an interim contact or an unscheduled visit at any time during the study. All interim contacts and unscheduled visits will be documented in the participants study records and visit e-CRFs.

Interim or unscheduled visits are AE-related visits in that health related reaction, effect, or abnormality is reported. Other examples of reasons for an interim or unscheduled visit not in response to an AE are:

- To get more trial drugs in cases of loss or misplacement.
- To ask questions and discuss problems with study compliance
- Interim examination - examination requested but no complaints or symptoms

5.5 Study Completion visit (Pregnancy loss or delivery)

A participant will be considered to have completed the study once there is a pregnancy loss or delivery at any time after randomisation and all relevant data is captured into the appropriate study completion CRF.

The following steps will be taken at the end of study visit

- ❖ Physical examination
- ❖ Evaluate compliance & ADE
- ❖ Complete all relevant documents
- ❖ Complete delivery e-CRF (*at delivery- Appendix viii*) and end of study visit e-CRF at completion of all study visits and data entry (*Appendix ix*) and other relevant source documents.

- ❖ Counselling and necessary referral (e.g Postpartum and family planning clinics)

Tables below lists all of the assessments and indicates with an “X” the visits when they are performed. All data obtained from these assessments must be supported in the patient’s source documentation. The Table indicates which data are entered into the database (D) or remain in source documents only (S) or both (SD).

Assessments that generate data for database entry and which are recorded on CRFs are listed using the CRF name (Enrollment, Visit, Study completion). Assessments that are transferred to the database electronically (e.g. laboratory data) are listed by test name.

Table 1: Study Visit Schedule

	Pre-treatment	Treatment (Enrollment and follow-up)																			Delivery			
Study Visit	0	1	2	3	4	5	6	7	8	9	10	11	12	13	14	15	16	17	18	19	20	21		
GA in weeks	6-11	12	14	16	18	20	22	24	26	28	29	30	31	32	33	34	35	36	37	38	39	40		
Screening	X	X	X	X	X	X	X	X	X															
Enrollment		X	X	X	X	X	X	X	X	X														
Follow-up			X	X	X	X	X	X	X	X	X	X	X	X	X	X	X	X	X	X	X	X	X	
End of study				X	X	X	X	X	X	X	X	X	X	X	X	X	X	X	X	X	X	X	X	

Table 2: Assessment schedule for study participants

Phase	Pre-Treatment	Treatment (Enrollment and follow-up)																	Delivery			
Study visit	0	1	2	3	4	5	6	7	8	9	10	11	12	13	14	15	16	17	18	19	20	21
GA in weeks	6-11	12	14	16	18	20	22	24	26	28	29	30	31	32	33	34	35	36	37	38	39	40
Inclusion/exclusion criteria (S)	X	X	X	X	X	X	X	X	X													
Written informed consent (S)	X	X	X	X	X	X	X	X	X													
Demographics/ PMH (SD)	X	X	X	X	X	X	X	X	X													
Concomitant medication (SD)	X	X	X	X	X	X	X	X	X	X	X	X	X	X	X	X	X	X	X	X	X	X
Body weight (SD)	X	X	X	X	X	X	X	X	X	X	X	X	X	X	X	X	X	X	X	X	X	X
Physical examination (SD)	X	X	X	X	X	X	X	X	X	X	X	X	X	X	X	X	X	X	X	X	X	X
Laboratory (SD) Hb +Urinalysis	X	X	X	X	X	X	X	X	X	X	X	X	X	X	X	X	X	X	X	X	X	X
Obstetric Scan (SD)						X																
Study Drug (SD)		X	X	X	X	X	X	X	X	X	X	X	X	X	X	X	X	X	X			
Adverse Events (SD)		X	X	X	X	X	X	X	X	X	X	X	X	X	X	X	X	X	X	X	X	X
End of study form (D)			X	X	X	X	X	X	X	X	X	X	X	X	X	X	X	X	X	X	X	X

6.0 PARTICIPANTS WITHDRAWAL & STUDY DISCONTINUATION

6.1 Premature patient withdrawal

Patients must be withdrawn from the study for any of the following reasons:

- Withdrawal of informed consent
- Use of any of un-prescribed medications
- Patients who discontinue study drug

Patients could also be withdrawn at any time if the investigator concludes that it would be in the patient's best interest for any reason. Protocol violations should not lead to patient withdrawal unless they indicate a significant risk to the patient's safety.

Patients may voluntarily withdraw from the study for any reason at any time. They may be considered withdrawn if they state an intention to withdraw, or fail to return for visits, or become lost to follow up for any other reason.

If premature withdrawal occurs for any reason, the investigator must determine the primary reason for a patient's premature withdrawal from the study and record this information on the Study Completion CRF.

Patients who are prematurely withdrawn from the study will not be replaced by newly enrolled patients.

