Randomisation code	A unique identifier assigned to each randomised patient, corresponding to a specific treatment arm assignment
Premature patient withdrawal	Point/time when the patient exits from the study prior to the planned completion of all study drug administration and assessments; at this time all study drug administration is discontinued and no further assessments are planned
Study drug discontinuation	Point/time when patient permanently stops taking study drug for any reason; may or may not also be the point/time of premature patient withdrawal
Variable	Information used in the data analysis; derived directly or indirectly from data collected using specified assessments at specified time points

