3.2 Sample Population

A total of 476 eligible pregnant HbSS and HbSC women from 12-28 weeks gestation will be enrolled and followed until delivery. Two study groups will comprise of approximately 238 HbSS or HbSC pregnant women who are confirmed with Haemoglobin phenotype testing by HPLC randomly assigned to each arm.

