7.6 Other concomitant treatment

Use of the following treatments is NOT allowed after the start of study drug:

- Any drug not prescribed.
- Herbal medications

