7.7 Study drug discontinuation

Study drug must be discontinued for a given patient if the investigator determines that continuing it would result in a significant safety risk for that patient. The following circumstances require study drug discontinuation:

- Emergence of severe adverse events: severe nausea/vomiting, allergy, severe pruritus, life threatening symptoms
- Persistent or heavy vaginal bleeding
- Abnormal laboratory values: Platelet count $\leq 50 \times 10^9/\text{ml}$
- In addition to these requirements for study drug discontinuation, the investigator should discontinue the study drug for a given patient if, on balance, he/she thinks that continuation would be detrimental to the patient's well-being.

Patients who discontinue study drug will be followed for the whole study duration until 36 weeks or delivery at which time all of the assessments listed for the final visit will be performed.

Reasons for Study Drug discontinuation should be completed, giving the date and primary reason for stopping the study drug under the relevant portion of the CRF.

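### Protocol 6.1 forces women who stop study drug or use un-prescribed medicines out of the study, contradicting 7.7 and follow-up to delivery, so the primary outcome can go unrecorded

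*Protocol*

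**What the plan says.** Protocol 6.1 opens with "Patients must be withdrawn from the study for any of the following reasons" and gives three: withdrawal of consent, use of un-prescribed medication, and discontinuing study drug. Neither of the last two carries a condition. Later in the same section a general sentence points the other way: "Protocol violations should not lead to patient withdrawal unless they indicate a significant risk" to the woman's safety. For a withdrawn woman, 6.1 asks the site to record the main reason. It does not ask for the pregnancy outcome, and she is not replaced.

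The protocol glossary treats premature withdrawal as leaving the study early and adds that "at this time all study drug administration is discontinued and no further assessments are planned". It defines drug discontinuation separately, as a point that "may or may not also be the point/time of premature patient withdrawal".

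Other protocol sections keep women in follow-up:
- 7.7: "Patients who discontinue study drug will be followed for the whole study duration until 36 weeks or delivery", with the final-visit assessments done at that time.
- 3.2: the 476 women "will be enrolled and followed until delivery". Section 3.4 repeats this for all women, without exception.
- 5.5: "A participant will be considered to have completed the study once there is a pregnancy loss or delivery at any time after randomisation".

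Section 7.6 introduces un-prescribed and herbal medicines with "Use of the following treatments is NOT allowed after the start of study drug". Section 11.1 gives failing to withdraw a woman who meets the withdrawal criteria as an example of a protocol violation.

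The SAP's intention-to-treat set is everyone randomised (5.2.1). Endpoints are not imputed in the main analysis (5.4).

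**The concern.** Stopping treatment and leaving follow-up are different events, and an intention-to-treat comparison depends on keeping them apart. Section 6.1 merges them. Where a site applies it together with the glossary, a randomised woman can lose her primary outcome because of something that happened after randomisation.

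That could bias the comparison if the loss is related both to arm and to prognosis. The documents show one possible route. Section 7.7 requires study drug to stop for vaginal bleeding that is heavy or persists, and section 3.9 lists vaginal bleeding among the potential adverse effects. The route operates only where a site follows 6.1 rather than 7.7. The documents give no reason for use of un-prescribed medicines to differ by arm.

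**Working it through.** **1. Women who stop study drug.** Section 6.1 requires withdrawal, and the glossary, using the same term as the 6.1 heading, plans nothing more after it. Section 7.7 requires continued follow-up of exactly these women. The glossary's own entry on drug discontinuation leaves withdrawal open. A site that follows 7.7 breaches 6.1 and 11.1; a site that follows 6.1 and the glossary breaches 7.7, 3.2 and 3.4. If an adverse event is unresolved at withdrawal, 8.4, which has events followed to resolution or permanence, is breached as well.

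**2. Women who use un-prescribed medicines.** Section 7.7 does not cover them. The conflict is with 3.2 and 3.4, and within 6.1 itself. Section 7.6 forbids these medicines, so their use departs from the protocol, and 11.1 counts participant compliance problems among violations. The general sentence in 6.1 rules out withdrawal for a violation without a significant safety risk; the 6.1 list requires it without that condition.

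**3. Where the outcome is recorded.** Pregnancy outcome, gestation and birthweight are on the delivery e-CRF (Appendix 08). The end-of-study form (Appendix 09), as printed, has a Withdraw category but shows no pregnancy-outcome field. Section 6.2 sets contact attempts and an open file for women who miss visits; nothing comparable is written for women withdrawn by rule. If the delivery form is not completed, the composite in SAP 2.2 is missing.

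**4. What the SAP then does.** She stays in the all-randomised set (5.2.1), deviations do not change the approach (6.2), and her endpoint is not imputed in the main analysis (5.4). She therefore contributes nothing to it. This is a consequence, not a written exclusion. Protocol 9.2 does write one, through a Primary Analysis set limited to women who completed 36 weeks or delivery, but the SAP does not carry that set over.

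**5. Scale.** No withdrawal rate is given, so only surrounding limits can be calculated.
- Plan's total: 396 × 1.2 = 475.2, rounded up to 476. The allowance is 476 − 396 = 80 women, and 80/476 = 16.8%.
- SAP 5.4 ignores outcomes missing in under 5%. If the outcome is expected for all 476, 0.05 × 476 = 23.8; 23/476 = 4.83% falls below the threshold and 24/476 = 5.04% does not.
- If the wording in 7.7 is read as ending at 36 weeks, follow-up stops before the 4 visits that protocol Table 1 schedules at 37, 38, 39 and 40 weeks.

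**6. Illustrative limits.** Assume 238 women per arm, 23 missing in all, and complete-case risks r of 0.10 (aspirin) and 0.20 (placebo). These are the plan's IUGR rates, borrowed for the composite. With m missing in an arm, of whom e had the event (0 ≤ e ≤ m), the all-randomised risk is [(238 − m) × r + e] / 238.

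| Missing (aspirin, placebo) | Lowest risk ratio | Highest risk ratio |
|---|---|---|
| 12, 11 | 0.0950 / 0.2370 = 0.40 | 0.1454 / 0.1908 = 0.76 |
| 23, 0 | 0.0903 / 0.2000 = 0.45 | 0.1870 / 0.2000 = 0.93 |
| 0, 23 | 0.1000 / 0.2773 = 0.36 | 0.1000 / 0.1807 = 0.55 |

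These ends are reached only if the missing women in an arm all had, or all lacked, the event. If they share the risk of the rest of their arm, the ratio stays 0.50.

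**7. What bias requires.** Assume no true effect (20% in both arms) and withdrawn women at twice the average risk, 0.40. With a share w lost, the observed risk is (0.20 − 0.40w)/(1 − w). Losing 20% of aspirin and 10% of placebo women gives 0.150/0.1778 = 0.84 instead of 1.00; 15% against 10% gives 0.1647/0.1778 = 0.93; equal loss leaves 1.00. All of these shares are assumptions.

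**The case against.** The strongest reply is that this is a wording conflict that sensible sites will resolve in favour of follow-up. Section 7.7 is the specific rule for women who stop drug and expressly continues follow-up, and 3.2 and 3.4 agree with it. The one plausible differential route, bleeding, is itself a 7.7 stopping reason. That limits how far bias can be predicted. It does not settle which rule prevails, because 6.1 is mandatory and 11.1 penalises ignoring it. With 15 sites, practice may differ.

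On un-prescribed medicines, neither 7.6 nor the examples in 11.1 call their use a violation by name, and a specific item could be read as an exception to the general sentence. That part does rest on inference, though the prohibition and the compliance example support it. The conflict with 3.2 and 3.4 remains on either reading.

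Some safeguards exist. Nothing restricts the delivery form to women still in the study. Protocol 5.1 has staff contact women who miss appointments. SAP 6.1 lists a postpartum visit form. SAP 5.4 plans baseline comparisons at 5% missing or more and says that imputation or weighting will be considered. But the contact duty concerns missed appointments, not withdrawal by rule, and no analysis recovers an outcome that was never collected.

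Two points stand. Section 5.5 defines completion and does not itself oblige every woman to complete, so its tension with 6.1 is weak. The risk-ratio limits would apply to any missing outcomes and do not isolate what 6.1 adds.

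**Conclusion.** The contradiction is real and needs correcting. Sites cannot comply with 6.1, the glossary, 7.7, 3.2, 3.4 and 11.1 together, and one permitted reading stops collection of the primary outcome. Loss is allowed by the text, not certain. The number of women affected, and the size and direction of any bias, are unknown. The figure of 23 women (4.8%) assumes that the outcome is expected for all 476; the risk-ratio limits rest on the assumed risks and missing numbers. The conclusion depends on none of these figures. It rests on conflicting mandatory instructions about whether the outcome behind the main comparison is collected.

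**What to change.** Amend the protocol so that the glossary, 6.1, 7.7, 8.4 and 11.1 agree, and so that stopping study drug or using an un-prescribed medicine does not by itself end outcome collection. Specifically:
- Collect pregnancy outcome, birthweight, gestational age and fetal or infant status to one week for every randomised woman, unless she withdraws consent to data collection.
- State that the delivery e-CRF is completed for women recorded as Withdraw on the end-of-study form.
- Align the end of follow-up in 7.7 with delivery, as in 3.2, 3.4 and 5.5.

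No view is offered on when treatment should stop.

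The documents do not state the trial's status. If follow-up continues, the cost is a short amendment and some tracing, using contact details that sites already collect (5.1). If it has ended, as the past tense in SAP 6.4 may suggest, an amendment recovers nothing; the remedy is to trace these outcomes from delivery records where consent allows.

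A separate, minor correction: weighting for missing outcomes in SAP 5.4 should use the inverse probability of observation, not of treatment.

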6.2 Loss to follow up

If a participant fails to appear for a scheduled visit, at least three attempts to contact her will be made over the subsequent 30 days. These attempts will be documented in the participant study file. Her file will remain open until the study close out.

For patients who are lost to follow-up (i.e. those patients whose status is unclear because they fail to appear for study visits without stating an intention to withdraw), the investigator should show "due diligence" by documenting in the source documents steps taken to contact the patient, e.g. dates of telephone calls, registered letters, etc.

If the participant does not return to the study before the study is closed, the end of study form will only be completed at the time of study closeout. The form will indicate that the participant was lost to follow up. The "lost to follow up" designation cannot be made for any participant until the closing date of the study.

7.0 STUDY PRODUCTS AND TREATMENTS

7.1 Study products:

- Aspirin
- Placebo

7.2 Study drug supply and resupply, storage, and tracking

Study drugs must be received by a designated person at the study site, handled and stored safely and properly, and kept in a secured location to which only the investigator and designated assistants have access. Upon receipt, all study drugs should be stored according to the instructions specified on the drug labels. Clinical supplies are to be dispensed only in accordance with the protocol.

The investigator must maintain an accurate record of supplies and dispensing of study drug in a drug accountability ledger. Monitoring of drug accountability will be performed by the field monitor during site visits and at the completion of the trial. Patients will be asked to return all unused study drug and packaging at the end of the study or at the time of study drug discontinuation.

7.3 Treatment assignment

At enrollment visit, all patients who fulfill all the inclusion/exclusion criteria will be given the lowest available number on the randomisation list. This number assigns them to one of the treatment arms. The investigator will enter the randomisation number on the enrollment log/CRF.

Each participant will receive a supply of the trial drugs. Participants will receive supplies in quantities anticipated to last until next visit. Research staff will show the participants how the drugs are to be taken. A participant will be instructed to return between scheduled visits to obtain more supplies if needed. A product dispensing log will be maintained by the clinic and field staff to track distribution of the trial drugs.

7.4 Treatment blinding

The trial is a double-blinded RCT study. Both treatments will be identically packaged and the pharmacist or an independent study site personnel will prepare and give the medication to the patient after randomisation. The investigator should remain blinded.

7.5 Dispensing the study drug and labeling

Each study site will be supplied by the unblinded study pharmacist with the study drugs in identically-appearing boxes. There will be a label with a unique randomisation code affixed to each of the boxes. Each unique code will correspond to a treatment arm. When the batch of study drug is delivered to a site, the receiving investigator (site coordinator), will notify the PI of receipt with a list of the randomisation codes received. The PI then notifies Sealed Envelope. Once a patient at a particular site is randomised, the code generated will correspond to the code on one of the boxes at that site. The investigator or research assistant will identify the study drug to dispense to the patient using the randomisation code on the label. Immediately before dispensing study drug to the patient, investigator staff will copy the code onto the source document (*Appendix x: Drug Accountability Form*) containing that patient's unique Study ID.

7.6 Other concomitant treatment

Use of the following treatments is NOT allowed after the start of study drug:

- Any drug not prescribed.
- Herbal medications

7.7 Study drug discontinuation

Study drug must be discontinued for a given patient if the investigator determines that continuing it would result in a significant safety risk for that patient. The following circumstances require study drug discontinuation:

- Emergence of severe adverse events: severe nausea/vomiting, allergy, severe pruritus, life threatening symptoms
- Persistent or heavy vaginal bleeding
- Abnormal laboratory values: Platelet count $\leq 50 \times 10^9/\text{ml}$
- In addition to these requirements for study drug discontinuation, the investigator should discontinue the study drug for a given patient if, on balance, he/she thinks that continuation would be detrimental to the patient's well-being.

Patients who discontinue study drug will be followed for the whole study duration until 36 weeks or delivery at which time all of the assessments listed for the final visit will be performed.

Reasons for Study Drug discontinuation should be completed, giving the date and primary reason for stopping the study drug under the relevant portion of the CRF.

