3.8 Laboratory evaluations

Standard clinical laboratory evaluations will be performed as follows:

Haematology:

- Full blood count (at enrollment and delivery)
- Hb fraction by HPLC (enrollment)
- Haemoglobin concentration with the Hemocue haemoglobinometer every 2 weeks from 20 weeks' gestation till delivery.

Urinalysis:

- Measurements will be performed by dipstick at every visit.

- Random/Spot urine protein to creatinine ratio (UPCR) will be ordered on a random urine sample if there is evidence of significant protein ($\geq 1+$) in the urine by dipstick.

Blood specimen will be collected in serum separator tubes for storage and use for future research.

All samples will be processed and analyzed at Synlab (an internationally accredited medical laboratory). Complete the ***laboratory tests request form (Appendix i)*** to accompany the sample to the lab, document date and time samples were taken in participant's case-note. Call courier services for sample pickup preferably within 6 hours of sample collection. Store samples at 4-8°C (refrigeration) immediately after collection before pickup; for not more than 12 hours. If any results are of clinical concern, a repeat sample will be collected at the next scheduled visit.

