3.9 Outcome measures

Primary outcomes:

- Birth weight below 10th centile for gestational age on the WHO INTERGROWTH- 21st birthweight charts
- Stillbirth
- Fetal death
- Miscarriage.

Secondary outcomes:

Pregnancy complications: Pre-eclampsia, Preterm delivery, retained placenta, placental abruption;

Maternal complications: Maternal death, frequency of crises, no of blood transfusions, incidence of urinary tract infection, respiratory tract infection, acute chest syndrome, and potential adverse effects such as vaginal bleeding, epigastric pain and heartburn.

Preeclampsia will be diagnosed based on ISSHP classification (17) if there is development of hypertension (either systolic blood pressure ≥ 140 mm Hg or diastolic blood pressure ≥ 90 mm Hg on two occasions at least 4 h apart) after 20 weeks gestation plus one of the following: proteinuria, thrombocytopenia or any multisystem complication.

Proteinuria will be defined as a dipstick test with $\geq 1+$ proteinuria ($\geq 30 \text{ mg dl}^{-1}$) on two occasions at least 4 hours apart, without any evidence of a urinary tract infection. Or UPCR $>300 \text{ mg/g Cr}$.

Thrombocytopenia will be defined as platelet count $< 100,000/\text{Ul}$.

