2.2 Endpoints

Primary

1. IUGR, perinatal death or miscarriage as a composite outcome

The occurrence of either IUGR, perinatal death or miscarriage will be the primary outcome.

IUGR will be defined as birthweight <10th centile for gestational age on the INTERGROWTH-21st birthweight charts, which is based on a healthy reference cohort from multiple countries, including Kenya(16). IUGR based on the Oken charts from a US national reference(17) maybe presented in sensitivity. A perinatal death refers to the death of a fetus after the age of viability (≥ 28 weeks' EGA), at delivery, or within the first week of life. A miscarriage refers to pregnancy, loss the death of a fetus before the age of viability (< 28 weeks' EGA). All participants will do an ultrasound scan at 20 weeks to estimate the gestational age of the pregnancy. Analysis will be by intention to treat.

Hypothesis:

1. We expect a 50% lower incidence of IUGR, perinatal death or miscarriage in the LDA (intervention) group compared to the placebo (control) group.

Secondary

1. The incidence of preeclampsia. Preeclampsia will be diagnosed based on ISSHP classification(18) if there is development of hypertension (either systolic blood pressure ≥ 140 mm Hg or diastolic blood pressure ≥ 90 mm Hg on two occasions at least 4 h apart) after 20 weeks gestation plus one of the following: proteinuria, thrombocytopenia, or any multisystem complication. Proteinuria will be defined as a dipstick test with 1+ proteinuria (≥ 30 mg dl $^{-1}$) on two occasions at least 4 hours apart, without any evidence of a urinary tract infection, or 2+ proteinuria or more on dipstick, or urinary protein creatinine ration >300 mg/g. Thrombocytopenia will be defined as a platelet count of $<100,000$ mm $^{-3}$.
2. The incidence of preterm delivery, defined as delivery at <37 weeks' EGA.
3. The incidence of:
 - a. Maternal death
 - b. Perinatal death
4. Number of sickle cell crises
5. Need for blood transfusion – identified based on whether the participant received a blood transfusion or not
6. Incidence of complications such as:
 - a. Urinary tract infection (UTI),
 - b. Lower Respiratory Tract Infection,
 - c. Acute chest syndrome,
 - d. retained placenta,
 - e. placental abruption; and
7. Incidence of potential adverse effects such as:
 - a. vaginal bleeding,
 - b. epigastric pain, and
 - c. heartburn

Analysis will be by intention to treat.

3 Study Methods

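### The mandatory platelet stopping limit in Protocol 7.7 is printed per ml, 500 times the trial's own thrombocytopenia cut-off; it was almost certainly meant per litre

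*Protocol*

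**What the plan says.** Protocol 7.7 introduces its list with the words "The following circumstances require study drug discontinuation", so the items on it are compulsory. The laboratory item is "Abnormal laboratory values: Platelet count $\leq 50 \times 10^9/\text{ml". It is the only numeric platelet limit for safety in either document.

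The other platelet threshold in the plan is diagnostic: thrombocytopenia is one of the features that, with hypertension, makes preeclampsia. Protocol 3.9 has "Thrombocytopenia will be defined as platelet count $< 100,000/\text{Ul". SAP 2.2 has "Thrombocytopenia will be defined as a platelet count of $<100,000$ mm $^{-3", and SAP Table 3 repeats that value.

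On timing, Protocol 3.8 schedules "Full blood count (at enrollment and delivery"; SAP Table 1 also marks a full blood count at follow-up, without a frequency. The follow-up and delivery e-CRFs (Protocol Appendices 07 and 08) label the platelet field in cells per ml.

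**The concern.** A stopping limit for low platelets should lie at or below the count at which the trial calls platelets low. The printed limit lies far above it, so the rule cannot separate a safe count from an unsafe one: all measured counts fall on the stop side.

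Three features of the protocol give the rule some weight.

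- Platelet count is not an exclusion criterion (Protocol 4.2).
- At enrolment the blood is drawn at the same visit at which the first three-week pack is handed over (Protocol 5.2). No step requires a platelet result before dosing begins, so 7.7 is the only written numeric check on that result.
- Protocol 11.1 counts as violations both a failure to withdraw a woman who meets withdrawal criteria and a failure to discontinue one who should have been discontinued. On the literal wording, any woman with a platelet result who stays on drug could be logged as a violation by a monitor working from the written protocol.

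**Working it through.** The limit is a stated threshold, not a calculated one, so the plan has no calculation to reproduce. The check is unit conversion.

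**Inputs**

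- Stopping limit as printed: 50 × 10⁹ per ml (Protocol 7.7).
- Thrombocytopenia cut-off: 100,000 per Ul (Protocol 3.9) and 100,000 per mm³ (SAP 2.2, SAP Table 3). Since 1 mm³ = 1 microlitre, the SAP confirms that Ul means microlitre, and the two documents agree.
- Conversions: 1 ml = 1,000 microlitres; 1 L = 1,000,000 microlitres.

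**As printed**

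- 50 × 10⁹ per ml ÷ 1,000 = 50,000,000 per microlitre.
- 50,000,000 ÷ 100,000 = 500 times the cut-off.

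**Read per litre**

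- 50 × 10⁹ per L ÷ 1,000,000 = 50,000 per microlitre.
- 50,000 ÷ 100,000 = 0.5 times the cut-off.
- The two readings differ by 50,000,000 ÷ 50,000 = 1,000.

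**In the e-CRF unit (cells per ml)**

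- Diagnostic cut-off: 100,000 × 1,000 = 1 × 10⁸ per ml.
- Stopping limit as printed: 5 × 10¹⁰ per ml.
- Stopping limit read per litre: 50,000 × 1,000 = 5 × 10⁷ per ml.

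**What the rule would do.** The counts below are assumed for illustration; they are not taken from the documents.

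| Count per microlitre | Count per ml | Stop under printed rule | Stop under per-litre rule |
|---|---|---|---|
| 150,000 | 1.5 × 10⁸ | Yes | No |
| 450,000 | 4.5 × 10⁸ | Yes | No |
| 1,000,000 | 1 × 10⁹ | Yes | No |

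The printed rule stops drug even at ten times the trial's thrombocytopenia cut-off. The per-litre rule stops drug at none of these counts.

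**The case against.** The strongest reply is that this is a typographical slip with little practical effect. A rule met by every result cannot be operated, so any clinician would read it per litre, and a single laboratory handles all samples. The literal error runs towards stopping too often: it would never oblige a site to keep a woman with low platelets on aspirin, and 7.7 separately lets the investigator stop drug on judgement. Exposure is narrow too. Drug ends at 36 weeks or delivery (Protocol 3.4), so the delivery count cannot trigger a stop; that leaves the enrolment count and whatever follow-up counts are done under SAP Table 1. No misapplied stop has been shown.

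All of that stands, and it limits the consequence. It does not make the text right: the rule works only if each reader silently replaces its unit, and the intended value has to be guessed.

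Two further points deserve an answer. The page was read by machine, so a misread unit cannot be wholly excluded. The e-CRFs also use ml for platelets, however, which makes that unlikely. It is also fair to say that cells per ml is a valid, convertible unit, used on the same forms for white cells, and that relabelling a form already in use can itself create mixed units. For that reason the e-CRF change is offered only as an option.

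**Conclusion.** The concern holds. As printed, the compulsory platelet limit is 50,000,000 per microlitre, 500 times the trial's own definition of thrombocytopenia, and 1,000 times the value it takes if read per litre. The conversion rests on reading Ul as microlitre, which the SAP's unit confirms. That per litre was intended is an inference, though a strong one: it gives 50,000 per microlitre, half the diagnostic cut-off, and so fits an item about abnormal values. The thrombocytopenia definitions in Protocol 3.9, SAP 2.2 and SAP Table 3 agree and need no change.

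This should be corrected because it is a decision threshold in a mandatory safety rule. The practical effect is probably small, and sample size, power, significance level and the primary endpoint are untouched. No data error is shown.

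**What to change.** In Protocol 7.7, replace the limit with a platelet count ≤ 50 × 10⁹/L (50,000 per microlitre), after the sponsor's clinicians have confirmed that this is the intended threshold. If sites would find it easier to have the limit in the e-CRF unit, the same value is 50 × 10⁶ per ml, and both forms can be printed side by side.

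As an optional safeguard, label the platelet fields of the follow-up and delivery e-CRFs in the unit used for the limit, or leave the label and state the conversion in the form's guidance. In either case, check the platelet values already entered for unit errors before deriving thrombocytopenia for the preeclampsia endpoint. In cells per ml, the diagnostic cut-off to apply is 1 × 10⁸.

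The cost is a one-line correction through the written amendment that Protocol 11.5 requires, plus a short data check if the option is taken. Design and analysis do not change.
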